#### 3.8.2 Clinical experience

The safety and clinical activity of Nintedanib either alone41-44or in combination with chemotherapy has been examined in a series of phase I studies conducted in patients with solid tumors.

The phase I dose selection studies have investigated the maximum tolerated dose (MTD), safety, and pharmacokinetics (PK) of Nintedanib. Based on the Phase I dose escalation trials with Nintedanib monotherapy, the maximum tolerated dose was defined to be 250 mg for twice daily dosing in Caucasians and 200 mg twice daily in Japanese patients with a manageable safety profile in advanced cancer patients. The studies revealed that Nintedanib is generally well tolerated with mild to moderate adverse effects such as gastrointestinal symptoms (nausea, diarrhea, vomiting, abdominal pain) and reversible elevations of liver enzymes. Initial signs of clinical activity included a complete response in a patient with renal cell carcinoma, 2 partial responses observed in patients with colorectal and renal cell carcinoma, and a disease stabilisation seen in 64% of patients for at least 2 treatment cycles (Mross et al)

Nintedanib has been studied in a randomized phase II maintenance trial following chemotherapy in relapsed ovarian cancer. Patients were randomized to either Nintedanib or placebo therapy for 36 weeks. The 36 week PFS rates were 16.3% in the Nintedanib group and 5% in the placebo group (HR 0.65; 95% CI, 0.42-1.02). The safety

profile was similar to what was reported in the initial trials. The proportion of patients with any grade 3 or 4 adverse events was similar between the groups (34.9% for Nintedanib vs. 27.5% placebo, p=0.49). However, there was more grade 3 or 4 hepatotoxicity in the Nintedanib group (51.2%) compared to placebo (7.5%, p<.001) This clinical activity has lead to development of a phase III trial in which Nintedanib or placebo in combination with paclitaxel and carboplatin in the first line treatment of ovarian cancer is being evaluated (ClinicalTrials.gov Identifier NCT01015118).

## 3.8.3 Nintedanib in Non-Small-Cell Lung Cancer (NSCLC)

The clinical activity of Nintedanib in advanced non-small cell lung cancer (NSCLC) was first demonstrated in a phase I trial in combination with pemetrexed in patients previously treated with a platinum-based regimen. In this dose escalation study of continuous Nintedanib with pemetrexed 500mg/m2 given on day 1 over a 21 day cycle, the MTD dose was 200mg BID in combination with pemetrexed. 1 patient achieved a complete response 44 days after starting treatment and disease stabilization seen in 50% as the best overall response. Median PFS was 5.4 months for all patients.

Nintedanib was also studied as a monotherapy in NSCLC patients in a phase II doubleblind study. In this study, patients were randomized to either Nintedanib 250mg BID or Nintedanib 150mg BID, continuous dosing and assessed at 6 week intervals until disease progression. Disease stabilization was achieved in 48% of patients and there was one confirmed partial response seen at the Nintedanib 250mg BID dosing. Tumour stabilisation was achieved in 46% of patients (ECOG 0–1 patients: 59%), with one confirmed partial response (250 mg BID).

The most commonly reported drug-related adverse events were nausea (57.5%), diarrhea (47.9%), vomiting (42.5%), anorexia (28.8%), abdominal pain (13.7%) and reversible alanine transaminase (ALT, 13.7%) and aspartate aminotransferase elevations (AST, 9.6%). The transaminase elevations were only seen at the higher dosing of the medication.

Based on the promising phase I and II results, there were two multicenter phase III studies evaluating Nintedanib 200mg BID in combination with chemotherapy in advanced NSCLC: the LUME-Lung 1 and LUME-Lung 2 trials. The preliminary results of both trials were recently presented at the Annual ASCO 2013 Meeting.

The LUME-Lung 1 trial evaluated Nintedanib plus docetaxel compared to placebo plus docetaxel in patients who progressed after first line therapy (ClinicalTrials.gov Identifier NCT00805194). The Nintedanib plus docetaxel group had a significantly PFS benefit (HR 0.79; CI: 0.68, 0.92; p=0.0019; median 3.4 vs 2.7 months) compared to the docetaxel alone. In subset analysis, the overall survival was increased in the adenocarcinoma histology (HR 0.83; p=0.0359; median 12.6 vs 10.3 month).

The LUME-Lung 2 trial compared Nintedanib plus pemetrexed compared to placebo plus pemetrexed in patients with advanced nonsquamous NSCLC in the second line setting (ClinicalTrials.gov Identifier NCT00806819). The study was stopped prematurely after 713/1300 planned patients enrolled based on a pre-planned futility analysis. Ongoing patients were unblinded and follow-up was continued. The primary endpoint of PFS was met with the Nintedanib plus pemetrexed group showing a slightly improved median PFS

of median 4.4 vs 3.6 months in the pemetrexed arm (HR 0.83, 95% CI: 0.7–0.99, p=0.04). There was a higher incidence of grade 3-4 adverse events in Nintedanib plus pemetrexed compared to the pemetrexed alone arm (58.5% vs 42.3%). Withdrawals due to adverse events were similar between both groups. The most common reported drug-related adverse events (all grades) were ALT elevations (42.9%), AST elevations (37.2%), nausea (36.9%), diarrhea (34.9%), fatigue (33.7%), and decreased neutrophil count (21.6%).

# 3.8.4 Rationale for Current Study

There is a clear rational to study more than one VEGF targeted agent in esophagogastric cancers as has been indicated by experience in other solid tumor malignancies and other targeted agents. There have been inconsistent benefits for targeted agents within the spectrum of GI malignancies, underscoring the need to evaluate each new promising agent independently in each tumor type.

For example, in GI malignancies, the EGFR tyrosine kinase inhibitors erlotinib and gefitinib have been inactive as single agents in adenocarcinoma of the colon, stomach, and esophagus. However in pancreatic cancer, erlotinib plus chemotherapy with gemcitabine yielded positive results, including a progression free and overall survival benefit. On the other hand, the EGFR targeted antibody cetuximab failed when combined with chemotherapy in pancreatic cancer. This is in contrast to the single agent activity of cetuximab seen in colon cancer.

It is clear that each new targeted agent, with individual variation in what specific targets are actually affected, needs to be evaluated in each solid tumor. Other than Human Epidermal Growth Factor Receptor (HER2), there are no validated treatment targets in esophagogastric cancer. Nintedanib is of particular interest in esophagogastric malignancies due to its ability to simultaneously target the VEGFR, PDGF, and FGFR pathways, which have been described and implicated in this disease.

# 4.1 OVERVIEW OF STUDY DESIGN/INTERVENTION

# 4.2 Design

This is a single institution, open-label, non-randomized, phase II evaluation of oral Nintedanib at 200mg twice daily, continuous dosing in patients with metastatic or recurrent esophagogastric adenocarcinoma.

Patients may have received up to one prior chemotherapy regimen for metastatic disease or up to two prior regimens if they previously received neoadjuvant/adjuvant chemotherapy or chemoradiotherapy for their initial localized disease. All patients must be able to provide informed consent.

See Section 10 for treatment schema.

#### 4.3 Intervention

32 patients will be enrolled on this clinical trial. Patients will receive Nintedanib 200mg twice daily continuously until disease progression, unacceptable toxicity, or serious intercurrent illness develops, or if patient consent is withdrawn.

Patients must have measurable or evaluable disease and undergo a computerized tomography (CT) or magnetic resonance imaging (MRI) scan of their chest and abdomen within 28 days of study enrollment, then at eight weeks, and every eight weeks thereafter (every 2 cycles). For the followup scans, a scheduling window of up to one to fourteen (1-14) days will be permitted. If a complete response is achieve and maintained for 12 months, patients with complete response will then be required to repeat CT or MRI evaluation every 4 months up to 5 years post complete response status, then every 6 months thereafter, with a scheduling window of one to fourteen (1-14) days. Response assessment will be by RECIST 1.1 criteria. The same imaging modality performed at baseline (CT or MRI) will be repeated at subsequent imaging.

Therapy will be administered in the outpatient setting, with each cycle consisting of 28 days of continuous therapy. The cycle start date will coincide with the physician visit date. A study diary will be completed by patients to ensure compliance with the study drug (Appendix I).

# 5.0 THERAPEUTIC/DIAGNOSTIC AGENTS

Substance (INN):	Nintedanib
Other names:	BIBF 1120
Pharmaceutical form:	Soft gelatine capsule
Source:	Boehringer Ingelheim Pharma GmbH & Co. KG
Unit strength:	100 mg and 150 mg capsules
Daily dose:	200 mg twice daily
Duration of use:	Continuous daily dosing; once cycle consists of 28 days. Patients are eligible for repeated treatment cycles in the absence of disease progression and undue adverse events (as per criteria in Section 9.2)
Route of administration:	Oral (swallowed)
Posology:	Twice daily (to be swallowed unchewed with a glass of water of about 250 mL with a dose interval of around 12 hours at the same times every day, usually in the morning and the evening after food intake)

# 6.1 CRITERIA FOR SUBJECT ELIGIBILITY

# 6.2 Subject Inclusion Criteria

- Pathologically or cytologically MSKCC confirmed esophagogastric adenocarcinoma.
- Metastatic diseases measurable or evaluable on a CT or MRI scan according to RECIST 1.1 criteria. Locally recurrent disease that is not amenable to potentially curative surgery or radiation therapy is also allowed. Lesions must be ≥10mm in size. Recurrent or metastatic disease within a prior radiation field is acceptable as long as the disease has progressed in the radiation field by RECIST criteria. See Section 12.2 for definition of measurable lesions.
- Patients are allowed to have had a maximum of 1 prior chemotherapy regimen for metastatic disease. Patients are allowed to have a maximum of two prior regimens if they previously received neoadjuvant/adjuvant chemotherapy or chemoradiotherapy for their initial localized disease.
- Patients aged 18 years or older.
- Life expectancy of at least 6 months.
- Karnofsky Performance Status (KPS) performance score ≥ 70%.
- Patients must be able to reliably take and swallow oral medications.
- Patients with prior deep vein thrombosis (DVT) or pulmonary embolism (PE) currently on anticoagulation regimen will be permitted.

Adequate bone marrow, liver, and renal function as assessed by the following:

- Hemoglobin  $\geq$  9.0 g/dL.
- Absolute neutrophil count (ANC) ≥ 1,500/mm^3.
- Platelet count  $\geq$  100,000/mm^3.
- Total bilirubin within normal limits, 0–1 mg/dL.
- AST and ALT< 1.5 times ULN. (For patients with liver involvement: AST and ALT≤ 2.5 ULN).
- International normalized ratio (INR) < 2, prothrombin time (PT) < 20 sec, and partial thromboplastin time (PTT) < 55 sec.

- Creatinine < 1.5 x the ULN or GFR<45 ml/min.

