# 6.3 Subject Exclusion Criteria

- HER-2 positive esophagogastric cancer. Patients with unknown HER2 status are permitted.
- Patients receiving any concurrent anticancer therapy or investigational agents with the intention of treating esophagogastric cancer. Last prior therapy must have been completed at least 2 weeks (14 days) prior to starting Nintedanib.
- Concurrent radiotherapy is not permitted for disease progression on treatment on protocol. However, symptomatic treatment for pre-existing non-target lesions would be allowed with approval from the principal investigator.
- Prior treatment with VEGFR inhibitor.
- Brain metastases or leptomeningeal disease.
- History of arterial thromboembolic (arterial blood clot) or hemorrhagic event with the exception of patients with pulmonary embolism stable on an anticoagulation regimen.
- Patients with a cerebrovascular accident or transient ischemic attack within the past six months.

- Patients on warfarin for any reason.
- Patient with known pre-existing interstitial lung disease.
- History or presence of clinically relevant cardiovascular abnormalities such as uncontrolled hypertension, congestive heart failure, New York Heart Association (NYHA) functional classification of 3, unstable angina or poorly controlled arrhythmia. Myocardial infarction within 6 month prior to the study entry.
- Patients with history of proteinuria grade  $\geq 2$ .
- Women of childbearing potential (WOCBP), or men who are able to father a child, unwilling to use a medically acceptable method of contraception during the trial and for at least three months after the end of active therapy.
- Women who are pregnant or breast-feeding.
- Persistence of clinically relevant therapy related toxicity from previous chemotherapy and/or radiotherapy. This does not include hemoglobin or other hematologic or laboratory criteria, as long as eligibility criteria are met as outlined in 6.1.
- Other malignancies within the past 5 years other than non-melanoma superficial skin cancer or carcinoma in situ of the cervix.
- Concurrent medical conditions or injury which may increase the risk of toxicity, including ongoing or active infection, history of significant bleeding disorder unrelated to cancer (congenital bleeding disorders, acquired bleeding disorders within one year), history of HIV-positive, or active or chronic hepatitis C and/or B infection.
- Known or suspected active drug or alcohol abuse.

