# 8.1 PRETREATMENT EVALUATION

To be completed within 2 weeks of study entry:

- History and physical exam including vitals, height, weight, performance status.
- Evaluation of concomitant medications and toxicity assessment.
- Serum pregnancy test for women of childbearing potential (WOCP) In addition, all WOCP should be instructed to contact the Investigator immediately if they suspect they might be pregnant at any time during the study participation.
- Laboratory evaluation including a complete blood count, PT/PTT, comprehensive chemistry panel (includes BUN, creatinine, ALT, AST, albumin, glucose, total protein, calcium, bilirubin, bicarbonate, sodium, chloride, potassium, alkaline phosphatase).

To be completed within 4 weeks of study entry:

- Electrocardiogram
- CT scan or MRI documenting all measurable or evaluable disease. All measurable lesions used to define response must be >10mm in size. The primary tumor is excluded. Lesions within prior radiation fields are permitted as long as these lesions have documented progression in size.

To be completed any time prior to starting therapy:

- Histological confirmation of esophagogastric adenocarcinoma prior to study enrollment.
- Available tumor tissue (20 unstained slides or tumor block) will be submitted for future molecular analysis (SEE SECTION 10 "Correlative Studies") but not be required prior to registration. Note: if tissue is depleted, patient will still be eligible after discussion with the PI.

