# 13.1 CRITERIA FOR REMOVAL FROM STUDY

If at any time, the patient develops progressive disease he/she will be taken off study and referred for alternative therapy. If at any time the patient develops unacceptable toxicity that fails to resolve after a maximum treatment delay of 4 weeks, he/she will be removed from study. Before being removed from the study, patients will be scanned to assess the response. If the off study scan shows progression of disease then the patient will be considered as a non-responder, while a CR or PR will be considered as response. A patient will be withdrawn from the study treatment in the following circumstances:

- Patient is no longer able to participate in the study (e.g. AE, surgery, concomitant diagnoses, concomitant therapies or administrative reasons); in such a case the Investigator's reason for patient's removal must be recorded in CRDB.
- Patient withdrawal of consents or election to discontinue participation in the trial.

- Significant deviation from the protocol or eligibility criteria; such patients will be considered protocol violations and removed from study.
- Non-compliance with study or follow-up procedures.
- Drug related AE(s) that have not resolved after 3 weeks of treatment interruption. Exception to this in patients who derive obvious clinical benefit according to the investigator's judgment could be considered upon discussion with Principal Investigator. The dose reduction scheme provided should be followed in this case.
- Repeat episodes of drug related toxicity despite dose reduction to Nintedanib 100mg twice daily dose.
- Documented progressive disease.
- Patients who become pregnant while on study.

As soon as a patient is withdrawn from the study treatment, the End of Treatment (EOT) visit has to be performed (not in case patient has withdrawn consent). Every effort should be made to follow-up patients in case an adverse event is still ongoing at the time of withdrawal.

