# 15.1 RESEARCH PARTICIPANT REGISTRATION AND RANDOMIZATION PROCEDURES

# 15.2 Research Participant Registration

Confirm eligibility as defined in the section entitled Criteria for Patient/Subject Eligibility.

Obtain informed consent, by following procedures defined in section entitled Informed Consent Procedures.

During the registration process registering individuals will be required to complete a protocol specific Eligibility Checklist.

All participants must be registered through the Protocol Participant Registration (PPR) Office at Memorial Sloan-Kettering Cancer Center. PPR is available Monday through Friday from 8:30am – 5:30pm at [contact]. Registrations must be submitted via the PPR Electronic Registration System (http://ppr/). The completed signature page of the written consent/RA or verbal script/RA, a completed Eligibility Checklist and other relevant documents must be uploaded via the PPR Electronic Registration System.

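### The GFR limb of the renal inclusion criterion points the wrong way and reverses eligibility for patients with creatinine at or above 1.5 x ULN

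*Combined protocol and SAP*

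**What the plan says.** In section 6.2 the laboratory requirements are introduced by "Adequate bone marrow, liver, and renal function as assessed by the following". The renal item in that list is "Creatinine < 1.5 x the ULN or GFR<45 ml/min". It is the only place in the protocol that sets a limit on creatinine or GFR.

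Four other sections bear on how the line operates:

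- **Section 6.3 (exclusions).** The one specifically renal item concerns proteinuria ("Patients with history of proteinuria grade" 2 or higher). The exclusion for residual toxicity from earlier treatment carves out laboratory values: "This does not include hemoglobin or other hematologic or laboratory criteria, as long as eligibility criteria are met as outlined in 6.1".
- **Section 8.1 (screening).** The laboratory work includes a "comprehensive chemistry panel (includes BUN, creatinine, ALT, AST, albumin, glucose, total protein, calcium, bilirubin, bicarbonate, sodium, chloride, potassium, alkaline phosphatase"). Creatinine is there; GFR is not listed.
- **Section 15.2 (registration).** Staff are told to "Confirm eligibility as defined in the section entitled Criteria for Patient/Subject Eligibility", and a protocol-specific checklist must be completed.
- **Section 13.1 (removal).** One ground for withdrawal is "Significant deviation from the protocol or eligibility criteria; such patients will be considered protocol violations and removed from study".

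**The concern.** A low GFR means poor kidney function. Under a heading that asks for adequate renal function, a GFR limb should be a floor, as the hemoglobin, neutrophil and platelet items are. Here it is a ceiling, and the 'or' makes it sufficient by itself, so a patient who fails on creatinine can qualify because GFR is also poor.

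Two different problems follow, depending on how the line is applied:

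- **Applied literally,** it can admit a patient with high creatinine and low GFR to continuous dosing at 200 mg twice daily. It also turns away a patient with high creatinine whose GFR is 45 ml/min or more.
- **Applied as evidently intended,** it lets that second patient in, but the patient then deviates from the written criterion and could be treated as a violation under section 13.1.

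Staff who must confirm eligibility against this section should not have to choose between its wording and its purpose.

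**Working it through.** The plan gives no figure to reproduce here, so the check is a truth table and a reading of the surrounding text.

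**Inputs.** Both limits, 1.5 x ULN for creatinine and 45 ml/min for GFR, come from section 6.2. Creatinine (cr) is in multiples of ULN and GFR in ml/min.

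**Rules compared.**

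- Written: eligible if cr < 1.5 or GFR < 45.
- Corrected: eligible if cr < 1.5 or GFR >= 45.

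**Boundary cells and two examples.**

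| cr (x ULN) | GFR | Written | Corrected | Changes? |
|---|---|---|---|---|
| 1.4 | 44 | eligible | eligible | no |
| 1.4 | 45 | eligible | eligible | no |
| 1.5 | 44 | eligible | not eligible | yes |
| 1.5 | 45 | not eligible | eligible | yes |
| 3.0 (example) | 20 | eligible | not eligible | yes |
| 1.6 (example) | 60 | not eligible | eligible | yes |

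In the four boundary cells, each rule admits 3 of 4, so a simple count hides the problem; 2 of the 4 change status. A wider grid, with creatinine 1.2, 1.49, 1.5 and 2.0 x ULN crossed with GFR 30, 44, 45 and 60, gives the same picture. The rules agree in all 8 combinations below 1.5 x ULN and disagree in all 8 at or above it.

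**Is the sign out of line with its neighbours?** The laboratory list contains 10 inequality signs:

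- Floors on quantities where low is bad: hemoglobin, ANC, platelets (3).
- Ceilings on quantities where high is bad: the two AST/ALT limits, INR, PT, PTT and creatinine (6).
- GFR: a ceiling on a quantity where low is bad (1).

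So 3 + 6 = 9 signs agree with the heading, and GFR alone does not.

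**Does anything else repair it?** The proteinuria exclusion sets no creatinine or GFR limit. The residual-toxicity exclusion hands laboratory values back to the inclusion criteria, which is where the error sits. The general exclusion for concurrent conditions that raise toxicity risk could catch some patients, but only by judgement. The toxicity-management tables in section 9.4 cover diarrhea, liver enzymes, and nausea and vomiting; none is renal. Creatinine is monitored on treatment, but that comes after exposure has begun.

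**The case against.** The strongest points on the other side are these.

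- **Conversion noise.** The sign was read from text extracted from the PDF. The coagulation line just before it ends in a stray markup tag, and section 9.4.2 appears to lack a sign before a bilirubin limit. No flipped sign has been shown, and the other signs in the list read sensibly, but a misread cannot be excluded. This point stands. It limits confidence to medium and makes checking the PDF the first step.
- **The intent is obvious.** Most oncologists would read the line as a floor, so literal admission of a patient with very poor renal function is unlikely. The two harms also need opposite readings and cannot arise from the same one. That is fair, but each reading produces one of the problems, and reading the line sensibly still means departing from the written criterion.
- **Few patients, and no stated renal hazard.** The cells in the table are logical combinations, not patients, and are not equally likely. The toxicities listed in section 11 are mainly gastrointestinal and hepatic, and no renal dose adjustment is described. This stands as a limit on what can be claimed: neither the frequency nor the clinical risk can be quantified from the documents.
- **Removal is speculative.** Section 13.1 speaks of significant deviations, and nothing shows that a patient who meets the intended criterion would be removed. Removal is therefore a possibility, not a prediction.
- **The checklist may already be right.** It is not shown, so this cannot be assessed.

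None of these points disputes that the line, as it reads, contradicts its heading.

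**Conclusion.** The concern holds. As written, the criterion gives the reverse of the evidently intended answer for every patient with creatinine at or above 1.5 x ULN, and makes no difference for anyone below that limit. The GFR limb matters only for patients who fail on creatinine, so it is wrong exactly where it is used.

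The conclusion assumes that the sign in the source PDF is the one in the extracted text, and that the heading states the purpose of the list. The corrected rule further assumes that 45 ml/min was meant as a floor. Whether it should be >= or > matters only at exactly 45, and the documents do not say.

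This should be fixed as an eligibility and safety error. No effect on the primary endpoint, the sample size or the decision rule has been shown.

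**What to change.** 1. Check the sign in section 6.2 against the source PDF.
2. If it stands, change the second limb to GFR >= 45 ml/min, with the sponsor confirming the threshold.
3. Make the Eligibility Checklist agree, and review any patient already registered on the strength of the GFR limb.

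While the line is open, it would be helpful, though not essential to the correction, to say how GFR is obtained at screening. The same edit could confirm whether a patient with GFR below 45 ml/min but creatinine below 1.5 x ULN is meant to be eligible. Correcting the sign alone leaves that patient eligible through the creatinine limb.

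The cost is one symbol, one or two optional clarifying sentences, and a check of the checklist and the affected registrations. Sample size and analysis are untouched.
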